4.3 Sample Size

This study will aim to accrue a total of 40 subjects with invasive breast cancer into both the placebo and treatment arms (80 patients in total). The diagnosis will be based on histopathological evidence. The number of subjects was chosen based on the estimated ability to provide meaningful information on breast cancer. For discussion of statistics and power analyses, please see Section 12.

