7.0 Drug Formulation, Availability and Preparation

7.1 Vandetanib

Availability

AstraZeneca Pharmaceuticals Investigational Products will pack, label, and supply the investigational product (IP) for this study. Tablets will be packed into white high-density polythene bottles with child resistant, tamper evident closures. Study drug must be kept out of the reach of children. Each bottle will contain 100 tablets. Patients will be supplied with sufficient amounts of tablets at each dispensing visit plus overage (2 week supply with 2 additional doses). Drug and placebo will be sent to the Investigational Drug Service (IDS) in the Department of Pharmaceutical Care at the University of Iowa. The IDS will perform randomization using randomization.com and provide identical packages of drug or placebo for distribution by the pharmacist in the cancer center. Randomization will not be stratified and will be performed in groups of eight patients and for the entire cohort. Packages will be sequentially numbered and distributed as patients are enrolled, such that when a patient is enrolled they will be given the lowest numbered package remaining. Package number and patient identification number will be recorded in the study database, and the package key will held by the IDS and released to the investigator on completion of the trial.

Vandetanib tablets must be taken whole or dispersed in water, without crushing. If tablets cannot be taken whole, the tablets can be dispersed in a glass containing 60 mL of non-carbonated water and stirred for approximately 10 minutes until the tablets are dispersed (will not completely dissolve). No other liquids should be used. The mixture should be swallowed immediately. To ensure the full dose is received, the patient should refill the glass with an additional half glass of water and mix with any remaining drug and drink it.

There are no food restrictions for the administration of Vandetanib tablets. Vandetanib tablets should be taken in the morning at about the same time each day with a glass of water.

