Appendix 3: Preoperative toxicity visit flowchart

Appendix 4
Randomized, Controlled, Double-Blinded Trial Investigating the Effect of Vandetanib on Cellular Markers of Proliferation and Apoptosis in Breast Cancer

[name], PhD

INSTRUCTIONS FOR THE PATIENT: This is a monthly calendar on which you are to record which days you have taken your Vandetanib. Be sure you have enough calendars to last until your next appointment. If you develop any side effects from the pill, mark this on the calendar.
Bring the unused pills and your calendars with you at your next appointment
This diary is for your **Vandetanib** only

If you have any questions contact: _____

Telephone: _____

Your next appointment is: _____

VANDETANIB DIARY 300 mg daily

Week of	Sunday	Monday	Tuesday	Wednesday	Thursday	Friday	Saturday
Week of	Sunday	Monday	Tuesday	Wednesday	Thursday	Friday	Saturday
Week of	Sunday	Monday	Tuesday	Wednesday	Thursday	Friday	Saturday
Week of	Sunday	Monday	Tuesday	Wednesday	Thursday	Friday	Saturday
Week of	Sunday	Monday	Tuesday	Wednesday	Thursday	Friday	Saturday

Patient's signature: _____ date: _____

Appendix 5
Data and Safety Monitoring Plan

HCCC Clinical Trial Data and Safety Monitoring Plan (DSMP)

Date: 2/19/2013

IRB#: 201301763

Study Title: A Randomized, Double-Blind, Placebo-Controlled Trial Investigating the Effect of Vandetanib on Cellular Markers of Proliferation and Apoptosis in Invasive Breast Cancer

Principal Investigator: [name], PhD

Co-Investigators:

[name] Department of Surgery

[name] Department of Surgery

[name] Department of Internal Medicine

[name] Department of Pathology

[name] Biostatistician

All investigator-initiated protocols will be subject to ongoing monitoring of accrual, subject eligibility, protocol modifications and continuing reviews. Active studies will be audited for the DSMC by the CRSO, following guidelines based on level of risk to subjects. Audits will be conducted by reviewing subject files provided by clinical research coordinators, as well as original source documentation provided by online medical records and research pharmacists. The CRSO will review adverse events, eligibility of subjects, and adherence to the IRB- and PRMC-approved protocol. Protocols found to have discrepancies will be require a response from the PI and an action plan for correcting identified deficiencies. The DSMC will provide a schedule of audit and report dates if requested. **Type of Clinical Trial (check all that apply):**

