Investigator-initiated (Iowa)

Investigator-initiated, multi-center (non-Iowa)

- Is this study monitored by an outside DSMB? Yes No

Compassionate-use drug protocol

Pilot study

Phase I

Phase I/II

Phase II

Phase III

Phase IV

Study risk-level (refer to attached risk-level assessment for this study):

Level 1—low risk of morbidity or death, * <<1% of death or any adverse event

Level 2—risk of death* <1% or any adverse event 1% – 5%

Level 3—risk of death* 1% – 5% or grade 4 – 5 SAE 1% – 5%

Level 4—risk of death* >5% or grade 4 – 5 SAE >15%

Drugs being used on a “compassionate” basis

** Risk of death” refers specifically to 100-day treatment-related mortality*

The following additional documents will be included in the DSMP for this study:

- A subject eligibility check-list (inclusion / exclusion criteria), which will be available in OnCore, the HCCC CTMS
- A list of expected toxicities and stopping rules for suspension of accrual secondary to adverse events and safety parameters
- A signed and dated statement from the Principal Investigator(s) declaring any conflict of interest (or lack thereof) with a description of how a conflict of interest will be monitored to enhance transparency
- The Human Subjects application will be obtained from HawkIRB
- Future Continuing Review and/or Modification forms will be obtained from HawkIRB
- For multi-centered trials, a detailed description of the procedures in place at each center that enable communication between participating centers such that the PI is aware of the status of participating subjects including the immediate (<24hours – week day) awareness of grade 4 – 5 SAE / death

Risk Level 3

- An independent Study Monitor, or the DSMC Chair (or his designee), will review study data (provided by the PI and CRSO) and communicate with the PI at least twice yearly. The proceedings of this meeting will be summarized by the CRSO in a brief letter to the PI, a copy of which will be forwarded to the DSMC.
- Principal Investigator will provide a QUARTERLY report to the Study Monitor and the CRSO for the DSMC, or data may be obtained from OnCore:
 - Quarterly patient accrual data
- Copies of all Serious Adverse Events will be reported to the CRSO as per DSMC reporting guidelines.
- CRSO will conduct a BIANNUAL audit of at least 25% of the subjects' research charts, and will report the results to the DSMC. Audits will:
 - Validate eligibility of patients accrued to the study

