 - Check for the presence of a signed informed consent
 - Determine compliance with protocol methodology
 - Determine whether SAEs are being reported to internal and external regulatory agencies
 - Compare veracity of data in the research record with the primary source documents
 - Review investigational drug processing and documentation.

Assess cumulative AE/SAE reports for trends and compare to study stopping rules.

Routine Adverse Event Reporting

Routine reporting of adverse events to the DSMC via the CRSO is described in Table 1:

Table I: Routine Reporting of Adverse Events

Attribution	Adverse Event				
	Grade 1	Grade 2	Grade 3	Grade 4	Grade 5
Unrelated	Not required	Not required	CRSO	CRSO	CRSO
Unlikely	Not required	Not required	CRSO	CRSO	CRSO
Possible	CRSO	CRSO	CRSO	CRSO	CRSO
Probable	CRSO	CRSO	CRSO	CRSO	CRSO
Definite	CRSO	CRSO	CRSO	CRSO	CRSO

Eligibility Criteria:

- Patient with core biopsy, pathology demonstrating invasive breast cancer, with planned surgical excision
- Female gender. There is an incidence of male breast cancer, but it is unclear if the etiology is the same and inclusion of males could confound results.
- Age ≥ 18 . Breast cancer, while not restricted only to adult women, is rare in the younger population.
- ECOG performance status ≤ 2 .
- Life expectancy of greater than 6 months.
- Patient able to willingly provide informed consent to participate

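### The plan gives the Study Monitor and DSMC no adverse-event data by arm during the trial, so harm confined to vandetanib is diluted in a pooled review and cannot be told from background

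*Combined protocol and SAP*

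**What the plan says.** The trial is double-blind, with 40 patients planned per arm (section 4.3). Section 7.1 states that "the package key will held by the IDS and released to the investigator on completion of the trial".

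Safety data reach the reviewers as follows:

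- Section 11.1 has the PI maintain a summary table of adverse events for the audits.
- Appendix 5, Risk Level 3, has the monitor or the DSMC Chair (or designee) look at what the PI and CRSO supply: "will review study data (provided by the PI and CRSO) and communicate with the PI at least twice yearly".
- The one item listed for the PI's quarterly report is "Quarterly patient accrual data".
- The twice-yearly CRSO audit is also to "Assess cumulative AE/SAE reports for trends and compare to study stopping rules".

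No section calls for a tabulation by arm, coded or open, or gives the monitor or DSMC the key. The only unblinding described before completion is in section 11.2.4: the drug supplier will ask for the code, or for unblinding of serious events that need expedited reporting.

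**The concern.** A concurrent placebo group is the best means of separating drug toxicity from events due to the cancer, to anxiety or to the surgical pathway. Several toxicities listed as very common in section 11.2.4 (nausea, fatigue, headache, poor sleep) could also arise in untreated women awaiting cancer surgery. The plan rates the study risk level 3 and names QT prolongation and ventricular arrhythmia among the drug's major toxicities (section 7.1).

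The blinded PI cannot split the adverse-event table by arm, and nobody else is asked to. The person charged with looking for trends therefore has a total and no comparator. If toxicity on vandetanib were well above placebo, the review could miss it while patients were still being enrolled.

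**Working it through.** The documents give no probability of detecting a harm, so there is no figure of the plan's to reproduce. The event rates below are my assumptions.

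**1. Dilution.** With 1:1 allocation, pooled rate = (vandetanib rate + placebo rate) / 2.

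| Vandetanib | Placebo | Pooled | Pooled as share of vandetanib rate |
|---|---|---|---|
| 10% | 0% | 5% | 50% |
| 10% | 2% | 6% | 60% |
| 10% | 5% | 7.5% | 75% |
| 25% | 5% | 15% | 60% |

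The rate is halved only when placebo has no events. In that case 10% on vandetanib reads as 5%, the top of the 1–5% band that Appendix 5 uses for grade 4–5 serious events at risk level 3.

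**2. Can a pooled count show the harm?** Take a look at 40 patients, half of planned enrolment. Section 7.1 says "Randomization will not be stratified and will be performed in groups of eight patients and for the entire cohort". If each group of eight splits 4:4 (my assumption), 40 patients are five full groups, 20 per arm.

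- Harmful case, 25% v 5%: expected events 20 × 0.25 + 20 × 0.05 = 5 + 1 = 6.
- Equal case, 15% v 15%: expected events 20 × 0.15 + 20 × 0.15 = 3 + 3 = 6.

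Summing two binomial counts exactly:

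| Pooled events of 40 | 25% v 5% | 15% v 15% |
|---|---|---|
| 6 or more | 57.4% | 56.7% |
| 8 or more | 23.7% | 24.4% |

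Neither cut-off separates the two cases.

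**3. Can coded arm counts show it?** Let X and Y be independent binomial counts with n = 20 per arm. A reader of an A/B table does not know which arm is vandetanib, so a gap in either direction must count. P(|X − Y| ≥ 4) is the sum of P(X = x) × P(Y = y) over all pairs at least 4 apart.

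| True rates | Gap of 4 or more, either direction |
|---|---|
| 25% v 5% | 58.5% |
| 15% v 15% | 11.8% (5.9% each way) |
| 15% v 5% | 20.6% |
| 10% v 10% (same pooled rate as 15% v 5%) | 6.3% |

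Coded counts separate a large excess from no excess. They separate a moderate one only weakly.

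**4. Does the supplier's unblinding route fill the gap?** Section 11.2.4 limits expedited reports to unexpected grade 4–5 events at least possibly related to vandetanib. QTc prolongation is on the plan's own list of known risks, so as an expected toxicity it falls outside. Section 11.1 has the DSMC review every expedited report, but nothing says that these reach it unblinded.

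**The case against.** Several stronger readings are tempting, and the documents do not support them.

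- *The DSMC is barred from the key.* Section 7.1 fixes release to the investigator and is silent on the DSMC. The gap is an omission.
- *All the monitor's data come from blinded people.* The CRSO is also a source. Appendix 5 says "Active studies will be audited for the DSMC by the CRSO", drawing on "original source documentation provided by online medical records and research pharmacists", and nothing says that the CRSO is blinded. Equally, nothing gives the CRSO the key or asks for a comparison by arm.
- *No one can be unblinded before the end.* The supplier's route exists, though it is narrow and does not lead to the monitor.
- *The monitor sees accrual only.* Adverse events travel separately. Grade 3–5 events of any attribution, and at least possibly related events of any grade, go through the CRSO to the DSMC.
- *Harm is always halved.* That needs a zero placebo rate. Near zero, a monitor who knows the 1:1 ratio can double the pooled rate, and arm data add little.

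Other points also carry weight. Safeguards for the individual patient, such as stopping rules for severe toxicity and the preoperative EKG and laboratory tests, do not depend on arm. Section 10.1 expects few severe reactions over so short a course. Detection at this sample size is modest: even the expected split of 5/20 v 1/20 has a two-sided Fisher p of 0.18. The tick boxes that would show whether an outside DSMB is used cannot be read in the text available to me, so another body's role is uncertain.

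A related gap limits what arm data can do. Appendix 5 promises rules for suspending accrual, but its Stopping Rules section covers only individual withdrawal, with no count or rate. Those passages must be reconciled.

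These points narrow the concern. They do not supply the missing comparator where background events occur.

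**Conclusion.** The concern holds as a gap in the monitoring plan: nothing in it puts safety data by arm before the monitor or DSMC during the trial. Harm confined to vandetanib is diluted in a pooled rate, by half at most under equal allocation, and cannot be told from background when background is above zero. In the illustration a pooled review does not distinguish 25% v 5% from 15% v 15%, while a coded split flags them with probability 58.5% and 11.8%. At 15% v 5% the gain is smaller, about 21% against 6.3% for equal arms at the same pooled rate.

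These figures rest on assumed event rates, a 20:20 split at the look and an illustrative trigger of four events. That the review is pooled is inferred from the plan's silence. The change is worth making for patient safety. The Ki-67 analysis is not affected.

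**What to change.** Add a paragraph to Appendix 5, Risk Level 3:

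- The IDS gives a coded (A/B) allocation list to the Study Monitor or DSMC Chair, or to the CRSO acting for the DSMC. It does not go to the PI, the clinical team or the marker readers.
- That person links the list to the adverse-event and serious-event reports, drug discontinuations and QTc values already collected, and tabulates them by coded arm for the existing twice-yearly review.
- The monitor or DSMC Chair may ask the IDS to decode.

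The linkage has to sit with the monitor or CRSO, because no section gives the IDS adverse-event or QTc data.

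The cost is a paragraph of text, a list that the IDS can produce from the key it holds, and a little linkage work before each review. One or two people outside the study team would see coded groups. No patient visit or test is added.

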4.1.2 Exclusion Criteria

- Prolonged QT interval (QTc > 480 milliseconds) on screening EKG or congenital long QT syndrome
- Any concomitant medications that are known to be associated with Torsades de Pointes or QT elongation (see appendix 2).
- Hypertension not controlled by medical therapy (systolic BP greater than 160 mmHg or diastolic blood pressure greater than 100 mmHg).
- Patients taking metformin or digoxin. History of arrhythmia (multifocal premature ventricular contractions, bigeminy, trigeminy, ventricular tachycardia), which is symptomatic or requires treatment (CTCAE Grade 3), symptomatic or uncontrolled atrial fibrillation despite treatment, or asymptomatic sustained ventricular tachycardia. Patients with atrial fibrillation controlled by medication are permitted.
- Significant cardiac event (e.g., myocardial infarction), superior vena cava syndrome, New York Heart Association (NYHA) classification of heart disease ≥ 2 within 12 weeks, or presence of cardiac disease that in the opinion of the Investigator increases the risk of ventricular arrhythmia.
- Serum calcium or magnesium outside the institutional range of normal.
- Serum Potassium < 4.0 mmol/L or above 5.0 mmol/L
- Creatinine clearance < 50 ml/min
- PT > 12 seconds or PTT > 31 seconds
- Platelet count $< 100,000$
- Serum bilirubin greater than 1.5 mg/dl
- Alanine aminotransferase (ALT) > 50 U/L, aspartate aminotransferase (AST) > 65 U/L, or alkaline phosphatase (ALP) > 250 U/L
- Any cytotoxic treatments, such as neoadjuvant chemotherapy, planned before subsequent surgical procedure.
- Previous exposure to Vandetanib
- Previous enrollment or randomization in this study.
- Involvement in the planning and /or conduct of the study (applies to both Astra Zeneca staff and staff at UIHC).
- Previous or current malignancies of other histologies within the last 5 years, with the exception of in situ carcinoma of the cervix, and adequately treated basal cell or squamous cell carcinoma of the skin.
- Patients who have received prior surgical site radiation.
- Patients on CYP3A4 inhibitors or inducers (see appendix 1).
- Inability to test core biopsy for study markers
- Pregnancy or lactation at the time of study entry. (**Note: Pregnancy testing must be performed within 2 weeks prior to randomization according to institutional standards for women of childbearing potential.**)

Toxicities

Very Common (experienced by more than 10% of patients taking Vandetanib)

Headache
Diarrhea
Nausea/vomiting
Constipation
Decreased appetite,
Rash
Dry skin
Hypertension
Trouble sleeping
Weakness
Fatigue

Common (Experienced by 1 – 10% of patients taking Vandetanib)

QTc prolongation
Abnormal taste in mouth
Abdominal pain
Mouth swelling
Dry mouth
Weight loss
Elevated liver function tests
Anorexia
Hypokalemia
Hypocalcemia
Dehydration
Hypomagnesemia
Skin changes
Acne
Hair loss
Nail disorders
Mild nose bleed
Proteinuria
Kidney stone
Visual problems
Depression
Anxiety

Uncommon (Experienced by fewer than 1% of patients taking vandetanib)

Heart failure
Chest pain
Pancreatitis
Thrombocytopenia
Severe skin disorder
Seizure
Shortness of breath
Hypokalemia

Stopping Rules

Subjects will continue Vandetanib up to and including the morning of surgery. The time frame from clinic visit until definitive surgery will be a minimum of 2 weeks and the maximum of 4 weeks. Subjects will be evaluated for study withdrawal if noncompliant with requirement for therapy (at least 80% of doses), or if they are experiencing drug related toxicity. Patients may withdraw from the study at any time for any reason without effecting treatment of their breast cancer.
